# 1 INTRODUCTION

## 1.1 Study Rationale

Real world evidence (RWE) studies offer an opportunity to gather information of a marketed product in real-world heterogeneous populations that can complement clinical evidence, consumer insight data, and post-marketing surveillance. Real world data (RWD) generation is increasingly important in determining effectiveness outside of the tightly controlled conditions of randomized controlled trials (RCTs), that do not always reflect real-world patient populations, limiting their generalizability and external validity (Sherman et al., 2016).

This decentralized study is designed to generate real world data from subjects with cough associated with the common cold, evaluating the effects in two arms with commercially available cough syrups on health-related quality of life. Arm 1 includes one cough syrup (which can be used day or night) and Arm 2 includes the daytime cough syrup and a nighttime cough syrup.

Robitussin Maximum Strength Cough and Chest Congestion DM (Dextromethorphan HBr, USP 20 mg; Guaifenesin, USP 400 mg) and Robitussin Maximum Strength Cough and Chest Congestion DM + Robitussin Maximum Strength Nighttime Cough DM (Dextromethorphan HBr, USP 30 mg; Doxylamine Succinate, USP 12.5 mg) are marketed cough and congestion syrups used for treatment of cough associated with common cold. Although this is a non-life-threatening condition, it impacts individuals' ability to function normally in day-to-day activities (physical, social, occupational, and emotional).

Based on a large national on-line survey conducted in the United States (ACHOO survey) (Blais et al., 2015, Dicpinigaitis et al., 2015), Cough was the most common cold symptom (73.1%) and had a delayed onset (typically 1–5 days after cold onset) and a long duration (>6 days in 35.2%). Nasal congestion and cough were the most bothersome symptoms (Blais et al., 2015). Overall, 93% of survey participants reported sleep difficulty (slight to extreme) during a cough/cold. Among all respondents, 57% reported cough or nasal congestion as the symptoms making sleep difficult (Dicpinigaitis et al., 2015). In a similar RWE study, it was demonstrated that associated cold symptoms like blocked nose can impact overall quality of life and also that treatment can provide clinically meaningful improvements in QoL.

This study will generate data to support the effectiveness of the Robitussin syrups in the real-world setting to suppress cough among individuals with common cold to understand how the effect can influence their quality of life.

## 1.2 Background

Dextromethorphan, guaifenesin, and doxylamine are included in the FDA OTC Drug Monograph for Cold, Cough, Allergy, Bronchodilator, and Antiasthmatic Drug Products, which ensures their safety and efficacy as non-prescription medications. Dextromethorphan is an antitussive that works by suppressing the cough reflex in the brain, making it effective for temporary relief of coughs due to minor throat and bronchial irritation, such as from the common cold. Doxylamine, an antihistamine, blocks histamine H1 receptors to relieve symptoms like sneezing, runny nose, and itchy eyes associated with hay fever, allergic rhinitis, and the common cold. Guaifenesin, an expectorant, helps thin and loosen mucus in the airways, making it easier to clear congestion through productive coughing. The FDA monograph provides clear usage guidelines, ensuring safe access to these medications for both adults and children without a prescription.

Dextromethorphan's clinical efficacy has been demonstrated in several studies. In Parvez (Parvez, 1996), three successive trials involving 451 adults showed that a single 30 mg dose significantly reduced cough counts compared to placebo, with differences ranging from 19% to 36% ( $P < 0.05$ ). Cough counts were measured using cough acoustic signals, and the studies reported a net difference of 8-10 coughing bouts every 30 minutes. In a meta-analysis (Pavesi, 2001) of 710 subjects, a single 30 mg dose of dextromethorphan was tested using continuous cough recording over three hours. This study measured cough bouts, components, effort, intensity, and latency. The average treatment difference was 12% to 17% in favor of dextromethorphan for cough bouts ( $P$  value = 0.004), cough components ( $P$  value = 0.003) and cough effort ( $P$  value = 0.001), with an increase in cough latency ( $P$  value = 0.002). These studies reflect dextromethorphan's long-standing reputation as a reliable, non-prescription treatment for acute cough, complementing its well-established role in OTC medications.

The efficacy of guaifenesin as an expectorant has been demonstrated in studies involving both acute upper respiratory tract infections (URTIs) and chronic respiratory conditions such as chronic bronchitis. In a study by Robinson and colleagues (Robinson, 1977), guaifenesin was shown to significantly improve symptoms in patients with acute URTIs based on subjective patient assessments. Compared to placebo, guaifenesin reduced cough frequency and intensity at 48 and 72 hours ( $p < 0.01$ ), and it also decreased chest discomfort at 24, 48, and 72 hours ( $p < 0.01$ ). Additionally, in patients with productive coughs, guaifenesin increased sputum volume at 48 hours ( $p < 0.01$ ) and made it easier to raise sputum at 24, 48, and 72 hours ( $p < 0.01$ ). Given its proven efficacy, guaifenesin holds a well-established position as an OTC expectorant, offering consumers an accessible and effective treatment for chest congestion.

The efficacy of doxylamine in alleviating symptoms of runny nose and sneezing associated with the common cold was demonstrated in a clinical study involving cold sufferers (Eccles, 1995). The study involved 688 patients with cold symptoms who were randomized to receive either doxylamine succinate 7.5 mg four times daily ( $n = 345$ ) or a placebo ( $n = 343$ ). Results showed that doxylamine significantly reduced runny nose scores ( $P < 0.01$ ) and sneezing scores ( $P < 0.001$ ) compared to placebo. These findings suggest that doxylamine is an effective antihistamine in managing cold-related symptoms.

Cough is a common symptom associated with upper respiratory infections, particularly those caused by the common cold, which is predominantly viral in origin. The common cold affects millions of individuals worldwide, leading to significant morbidity and healthcare resource utilization. While cough serves as a protective reflex, persistent or bothersome cough can adversely impact quality of life, sleep, and daily activities.

The common cold represents the most frequent human disease (Stein, 2017). Its most relevant definition is a common viral infection of the nose or throat, with symptoms such as sore throat, runny nose, sneezing, and nasal congestion, clear discharge (mucus) from the nose, and body aches (Hemila, 2017). The trajectory of common cold symptoms caused by viruses can vary among individuals but does generally follow a familiar pattern. Cold symptoms tend to peak at 1 to 3 days after first appearance, thereafter symptoms usually last from 3 to 10 days. The mucus appearance may also change during this period. For some people the symptoms of common cold may linger a few more days, especially runny nose, stuffy nose, and coughing.

Although common cold symptoms are usually mild, they represent a huge burden for society in terms of impaired QoL and economic losses (Passioti et al., 2014, Heikkinen and Jarvinen, 2003). While rhinoviruses are the predominant cause of the common cold, the aetiologic agent remains unknown in up to half of all upper respiratory tract infections (URTIs) (Stein, 2017).

For the common cold, only symptomatic treatments exist (Passiotti et al., 2014, Stein, 2017). Most people require no prescription medications or doctor visits but do use a variety of over-the-counter (OTC) medications for relief of symptoms.

1.3 Mechanism of Action/Indication

Dextromethorphan is a centrally acting cough suppressant, and its primary mechanism of action involves inhibiting the activity of the medullary cough center in the brainstem, which reduces the cough reflex.

Guaifenesin is an expectorant and its primary mechanism of action is to help loosen and thin mucus in the airways, making it easier to cough up and clear from the respiratory tract. It reduces sputum viscosity by increasing the volume and water content of the bronchial secretions, thereby facilitating the expectoration of sputum.

Doxylamine is an antihistamine, and its primary mechanism of action involves blocking histamine H1 receptors. By inhibiting these receptors, doxylamine reduces the effects of histamine, a chemical in the body that causes symptoms such as sneezing, runny nose, itching, and watery eyes as may occur with hay fever or other respiratory allergies.

Robitussin Maximum Strength Cough and Chest Congestion DM	Robitussin Maximum Strength Nighttime Cough DM
Active ingredients (in each 20 ml) and purposes Dextromethorphan HBr, USP 20 mg - Cough suppressant Guaifenesin, USP 400 mg - Expectorant	Active ingredients (in each 20 mL) and purposes Dextromethorphan HBr, USP 30 mg - Cough suppressant Doxylamine Succinate, USP 12.5 mg - Antihistamine
Uses 

Temporarily relieves cough due to minor throat and bronchial irritation as may occur with a cold

Helps loosen phlegm (mucus) and thin bronchial secretions to drain bronchial tubes

	Uses 

Temporarily relieves cough due to minor throat and bronchial irritation as may occur with a cold

Temporarily relieves these symptoms due to hay fever or other upper respiratory allergies:

runny nose

sneezing

itchy, watery eyes

itching of the nose or throat

controls the impulse to cough to help you sleep

## 2 STUDY OBJECTIVES AND ENDPOINTS

**Table 2-1 Study Objectives and Endpoints**

Each of the treatment groups will be analyzed separately; there is no comparison between the study groups (daytime product only and daytime/nighttime product combination).

Objectives	Endpoints
Primary	
To evaluate the over-time effects of Robitussin on QoL factors and common cold symptoms among individuals experiencing cough associated with common cold, following up to 8 days of treatment using WURSS-21.	Score change from Baseline to each treatment day in: 
 
• WURSS-21 total score
 
• WURSS-21 total symptom domain score
 
• WURSS-21 total QoL domain score
 
• Each of the WURSS-21 symptom scores (10 items in total)
 
• Each of the WURSS-21 QoL scores (9 items in total)
 

Secondary	
To evaluate the over-time effects of Robitussin on QoL factors among individuals experiencing cough associated with common cold, following up to 8 days of treatment, using specific QoL questions.	Score change from Baseline to each treatment day in: 
 
• social activities
 
• feeling self-conscious around people
 
• coughing in public
 
• falling asleep
 
• sleeping through the night
 
• energy
 
• motivation
 

To evaluate the over-time effects of Robitussin on specific QoL questions among individuals experiencing cough associated with common cold, following up to 8 days of treatment, using categorized QoL factors.	Score change from Baseline to each treatment day in: 
 
• Sleep quality
 
• Vitality
 
• Physical activities
 
• Social activities
 

Safety	
To record adverse events (AEs) during study period	Number and percent of patients reporting AEs or serious AEs (SAEs) while on treatment: 
 
• Related to product
 
• Not related to product
 

Exploratory	
Subgroup analysis for primary and secondary endpoints	Subgroups: 
 
• Excluding subjects who took concomitant medications that are known to have an impact on common cold symptoms
 

## 3 STUDY DESIGN

### 3.1 Overall Design

This is a longitudinal, randomized, decentralized, open-label study evaluating the effect on QoL factors in subjects with cough associated with the common cold in two arms using Robitussin Maximum Strength in a real-world setting. A sufficient number of adults (approx. 372) aged 18 and over with symptoms of common cold will be screened for eligibility. The study expects to enroll approximately 260 eligible subjects across the United States with a total of 200 subjects expected to complete the study, approximately 100 in each study group. Subjects will be randomized into one of two study groups (at a 1:1 ratio):

- Group 1 will take Robitussin Maximum Strength Cough and Chest Congestion DM
- Group 2 will take Robitussin Maximum Strength Cough and Chest Congestion DM + Robitussin Maximum Strength Nighttime Cough DM.

Subjects will be recruited through targeted advertising on social media channels. This study is entirely decentralized, and subjects will not be required to physically attend any on-site visits. All study data will be collected remotely through a study platform using the subject's own mobile device, tablet, or computer.

Detailed study procedures can be found in Section [5](#) of the protocol.

### 3.2 Scientific Rationale for Study Design

RWE studies reflect product use in everyday life. They offer the opportunity to gather information on currently marketed products to not only substantiate clinical evidence, but to gather information on participant quality of life from the target patient population.

The Wisconsin Upper Respiratory Symptom Survey (WURSS) is an evaluative illness-specific quality of life instrument, designed to assess daily the negative impact of acute upper respiratory infection, presumed viral (the common cold). WURSS-21 is the short version of this validated instrument. WURSS-21 includes a single question on a global severity score, a symptoms domain (10 items), a functional domain (9 items) and an overall question on improvement/deterioration since yesterday. While the WURSS-44 covers more symptoms, the WURSS-21 exhibits similar performance in terms of reliability, responsiveness, importance-to-patients, and convergence with other measures.

Subjects with cough associated with common cold, who seek to treat with study treatment (Robitussin) will complete WURSS-21 and a specific QoL questionnaire once per day. Study treatment use will be reported via electronic diaries (eDiary). These measures will provide information on the effects of Robitussin over the natural course of their cough associated with common cold. This supports evaluation of the daily effects that may be attributable to the study treatment.

#### Limitations of the study

Given the natural course of the common cold, data collected during this study may be confounded by the natural resolution of the disease. Within 24 hours of cold onset, most patients report an escalation in the number of symptoms they experience, including sore throat, nasal congestion, runny nose, and headache. Over the initial days of having a cold, sore throat appears to be most bothersome on day 1 followed by nasal congestion and then cough.

Given the natural course of the disease, making sure subjects have access to treatment when cough symptoms are at their peak will allow for subsequent QoL data capture, reducing the influence of confounding variables.

There is substantial evidence to show that different symptoms of common cold overlap during the natural course of the disease. Subjects may likely be using over-the-counter antipyretics/analgesics for fever and/or headache, which may influence their overall QoL and confound data collected. During this study patients will be prompted to report medications they take for symptom relief, along with any changes in medication over the course of their study participation, which will allow the study team to review collected data objectively. Subjects who report taking medication(s) known to have an impact on common cold symptoms will be excluded for subgroup analysis.

### **3.3 Justification for Dose**

Dosing instructions will be followed as listed on the study product commercial label.

### **3.4 End of Study Definition**

A subject is considered to have completed the study if they have completed all procedures and assessments of the study including the last scheduled procedure shown in the Schedule of Activities.

Subjects will have the option to discontinue treatment at their discretion, if they determine they no longer want treatment. The end of the treatment period per subject is tentatively defined as Day 7 but may vary based on the need/severity of cough (see section 5 for further details). At the end of study, each subject should complete an end of study survey including product satisfaction.

The end of study is defined as the last data collection from the last subject participating in the study.

## **4 STUDY POPULATION**

### **4.1 Type and Planned Number of Subjects**

Adult subjects aged 18 and over (inclusive), of any race/ethnicity, reporting symptoms of the common cold including cough and at least one other common cold symptom (scratchy throat, sore throat, nasal congestion or watery nasal discharge) onset within the previous 48 hours will be screened for enrollment into the study. No discrimination of any kind (e.g. social class, gender, skin color, ethnicity) should preclude eligible participants from participating in the study. The study will aim to recruit a diverse population representative of the US census.

Sufficient subjects will be screened in order to enroll approximately 260 eligible subjects (approximately 130 subjects per study group). This study assumes an approximate 30% drop out rate. A total of 200 subjects are expected to complete the study (approximately 100 subjects per study group, allowing for up to 30% dropouts). Potential participants will be recruited through targeted digital advertising campaigns.

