## 4.2 Statistical Analysis:

### *Sample size:*

The study will be sufficiently powered to demonstrate statistically significant differences between QoL parameters in changes from Baseline to each treatment day as measured by the WURSS-21 (primary objective). Further details on the sample size determination can be found in section 8.1.

This study can fulfill its objectives only if appropriate subjects are enrolled. All relevant medical and non-medical conditions should be taken into consideration when deciding whether a subject is suitable for this protocol. Subject eligibility to participate in the clinical study should be reviewed and documented by a delegated member of the investigator's study team before subjects are randomized in the study. The following eligibility criteria are designed to select subjects for whom participation in the study is considered appropriate.

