# 8 STATISTICAL CONSIDERATIONS AND DATA ANALYSES

## 8.1 Sample Size Determination

Sufficient individuals (approximately 372) will be screened to enroll approximately 260 eligible subjects assuming an estimated 23% drop out rate. It is believed that for this study, 200

completed subjects (100 per treatment group) are deemed sufficient to observe an improvement in the WURSS-21.

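### Protocol 4.1 claims 200 completers from 260 enrolled with up to 30% dropout, but 30% leaves 182; only the 23% in Protocol 8.1 and SAP 1.4 gives 200

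*Protocol*

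**What the plan says.** - **Protocol 4.1** plans to "enroll approximately 260 eligible subjects (approximately 130 subjects per study group"). It continues: "This study assumes an approximate 30% drop out rate". It then adds: "A total of 200 subjects are expected to complete the study (approximately 100 subjects per study group, allowing for up to 30% dropouts").
- **Protocol 8.1** says that enough people (about 372) "will be screened to enroll approximately 260 eligible subjects assuming an estimated 23% drop out rate". It then states that 200 "completed subjects (100 per treatment group) are deemed sufficient to observe an improvement in the WURSS-21".
- **SAP 1.4** repeats the 372, 260, 23% and 200 of Protocol 8.1.
- **Protocol 3.1** gives 372 screened, 260 enrolled and 200 completing, with no dropout rate.
- **Protocol 4.2** says "The study will be sufficiently powered to demonstrate statistically significant differences" and sends the reader to 8.1 for the details. Neither 8.1 nor SAP 1.4 gives an effect size, a standard deviation or a power.

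**The concern.** One planning quantity, the loss between enrolment and completion, has two values. One of them does not connect the two counts it is printed beside. Section 4.1 goes further than a loose estimate: it says that the completer target survives dropout of up to 30%.

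Anyone who tracks attrition against 4.1 would be misled. Dropout of 28%, for example, would look within plan, yet it leaves 260 × 0.72 = 187 completers.

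The number matters because 200 completers is the only quantity on which the documents rest their statement that the study is large enough.

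**Working it through.** **Inputs**

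- Enrolled: 260, or 130 per group (Protocol 4.1; the total also in Protocol 3.1, 8.1 and SAP 1.4).
- Completers: 200, or 100 per group (same sections).
- Dropout: 30% (Protocol 4.1); 23% (Protocol 8.1, SAP 1.4).
- Screened: 372 (Protocol 3.1, 8.1, SAP 1.4).

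**Formulas.** Completers = enrolled × (1 − dropout). Enrolment needed = completers ÷ (1 − dropout).

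**Step 1. Reproduce the plan's figure at 23%.** 260 × 0.77 = 200.2, and 130 × 0.77 = 100.1 per group. In reverse, 200 ÷ 0.77 = 259.7, which rounds up to 260. Protocol 8.1 and SAP 1.4 are consistent with themselves and with each other.

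**Step 2. Repeat at the rate in 4.1.** 260 × 0.70 = 182, and 130 × 0.70 = 91 per group. The shortfall is 200 − 182 = 18, or 9 per group, and 18 ÷ 200 = 9%.

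**Step 3. The tolerance that the counts allow.** 1 − 200/260 = 23.1%. Above that rate the target of 200 is missed.

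**Step 4. Enrolment that 30% would require.** 200 ÷ 0.70 = 285.7, so 286 (143 per group), which is 26 more than planned.

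**Step 5. Where the 30% might come from.** Two routes fit equally well:

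- Screening loss: 1 − 260/372 = 30.1%, and 372 × 0.70 = 260.4.
- Inflation by multiplication instead of division: 200 × 1.30 = 260.

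The documents do not say which applies, or whether either does. Step 5 also shows that the 23% cannot describe the step from screening to enrolment, although the sentence in Protocol 8.1 and SAP 1.4 attaches it there.

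**Step 6. Effect on precision, for scale only.** The documents specify no such calculation. Assume a one-sample t-test of change within one group, two-sided 5%, with every completer contributing one value:

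| | n = 100 | n = 91 |
|---|---|---|
| Change detectable with 80% power | 0.283 SD | 0.297 SD |
| 95% CI half-width | 0.198 SD | 0.208 SD |

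The interval widens by about 5%.

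**The case against.** The best defence is that the sections which carry the sample-size argument are sound. Protocol 4.2 defers to 8.1; 8.1 and SAP 1.4 agree at 23%; and 23% delivers 200. On this view the 30% is a stray figure in a descriptive section. That is fair as to where the error sits, and it rules out a stronger inference a reader might draw, namely that the basis for the sample size has failed or that the study is underpowered. No numerical power is stated, so none can be shown to be lost.

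Completers are also not the analysis set. Primary and secondary analyses use the mITT population, which needs one dose and one post-baseline questionnaire (Protocol 8.2.1, SAP 4.2.3). The repeated-measures model uses the available data without imputation (SAP 4.5.1.2, 4.5.2). Subjects randomized but never dosed are replaced (Protocol 4.2). Eighteen fewer completers therefore does not mean eighteen fewer subjects analysed. This stands, but the offset is partial and unquantified. To restore 200 completers at 30% dropout, replacement would have to add 26 subjects (286 − 260), and the documents give no expected number.

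The words for approximation in 4.1 do not close the gap. The section states an upper limit that the target is said to withstand, and at that limit the target is missed by 9%.

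Two further inferences are tempting and unsupported:

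- *That the 30% is the screen-failure rate under the wrong label.* The arithmetic fits, but so does 200 × 1.30, and no section states a screen-failure rate.
- *That 100 per group supports a stated detectable change of about 0.28 SD.* The plan specifies a mixed model on mITT data by day, not a one-sample test. Subjects who stop early finish their daily forms one day after the last dose (Protocol 5.5), and flagged entries made after stopping are excluded from the tables (SAP section 5). One hundred completers need not give one hundred values on the later days.

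**Conclusion.** The inconsistency is real and can be shown from the documents alone. With 260 enrolled, the plan reaches 200 completers only if dropout is at most about 23%. At the 30% in Protocol 4.1 it reaches 182, or 91 per group. The statement in 4.1 that the target allows for up to 30% dropout is wrong as written.

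The consequence is modest: 9 fewer completers per group, and about 5% wider intervals under the simple assumptions in the working, less whatever the mITT definition and the replacement rule recover. No analysis, endpoint or stated power changes. The arithmetic assumes that dropout in 4.1 means loss between enrolment and completion, which is how that section uses the term when it ties the rate to the completer count.

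**What to change.** Use one dropout rate in Protocol 4.1, Protocol 8.1 and SAP 1.4.

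1. **If 23% is the expectation**, replace both 30% figures in Protocol 4.1 with 23%. The 260 and 200 then stand everywhere.
2. **If 30% is the expectation**, carry it into Protocol 8.1 and SAP 1.4, and restate the expected completers as about 182 (91 per group) in Protocol 3.1, 4.1 and 8.1 and SAP 1.4. The sponsor should then confirm that 182 is still regarded as sufficient.

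Under either option, reword Protocol 8.1 and SAP 1.4 so that the dropout rate belongs to the step from enrolment to completion. If the 30% was meant as the loss from 372 screened to 260 enrolled, the sponsor should confirm this before it is labelled so.

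Both options cost wording only. Keeping 200 completers with 30% dropout would instead need 286 enrolled, 26 more subjects.
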